Trial objective(s)	Primary objective is to investigate whether the maximum concentration (C_{max}) and the area under the curve (AUC ₀₋₂₄) values for the different components in the transporter cocktail - digoxin (P-gP), furosemide (OAT1 and OAT3), metformin (OCT2, MATE1 and MATE2-K) and rosuvastatin (OATP1B1, OATP1B3 and BCRP) are similar or different in F4 graded liver fibrosis (cirrhosis) patients on standard therapy compared to healthy subjects.
Trial endpoints	Primary endpoints: C_{max} and AUC ₀₋₂₄ of rosuvastatin, digoxin, metformin, and furosemide
Trial design	Open label, single dose study
Number of patients treated	[REDACTED]

Number of patients per treatment group	NA
Diagnosis	Group 1: NA (healthy subjects) Group 2: Patients with compensated liver cirrhosis and advanced fibrosis grade F4 and hepatic impairment that meets the criteria for Child Pugh A Group 3: Patients with decompensated liver cirrhosis and advanced fibrosis grade F4 and hepatic impairment that meets the criteria for Child Pugh B
Main inclusion and exclusion criteria	
Inclusion:
 
Healthy subjects
 
○ Healthy male and female subjects according to the assessment of the investigator, as based on a complete medical history including a physical examination○ Age of 18 to 75 years (inclusive)○ Body mass index (BMI) of 18.5 to 35 kg/m² (inclusive) 
Liver cirrhosis patients
 
○ Male and female patients○ 18 to 75 years (inclusive)○ BMI of 18.5 to 40.0 kg/m² (inclusive)○ Inclusion of
a) Patients with compensated liver cirrhosis due to any underlying liver disease with advanced fibrosis (F4) and hepatic impairment that meets the criteria for Child-Pugh A who are on stable standard of care treatment (per local guidelines) for at least 4 weeks prior to study enrolmentb) Patients with decompensated liver cirrhosis due to any underlying liver disease with advanced fibrosis (F4) and hepatic impairment that meets the criteria for Child-Pugh B who are on stable standard of care treatment (per local guidelines) for at least 4 weeks prior to study enrolment○ Diagnosis of compensated liver cirrhosis/F4
- Historic (within 2 years) histological diagnosis of fibrosis stage F4 (NASH-CRN or METAVIR scoring) 
OR
 
- Current or historic increased liver stiffness of \geq 18 kPa by Fibroscan or 5 kPa by MRE 
OR
 
- Current or historic imaging of nodular surface with thrombocytopenia $<$ 150/nL 
OR
 
- Clinical signs of portal hypertension (at least one out of the following)

- Gastroesophageal varices (GEV)
- Splenomegaly (no hematological or infectious diseases, which could cause splenomegaly)
- Thrombocytopenia < 120/nL

AND

- No previous decompensation events

- Diagnosis of decompensated liver cirrhosis/F4

- Any of the above

AND

- At least one previous decompensation event

Exclusion:

Healthy subjects and F4 liver cirrhosis patients

- Subjects already taking digoxin, furosemide, metformin or rosuvastatin within 4 weeks of enrolment into the study
- Subjects with any other condition that would preclude administration of digoxin, furosemide, metformin or rosuvastatin (i.e., contraindicated as per Summary of Product Characteristics (SmPC)), such as hypersensitivity to active ingredient or any of the excipients or to sulphonamides, hypovolaemia or dehydration, and partial obstructions of urinary outflow (e.g., prostatic hypertrophy)
- Any finding in the medical history or medical examination (including blood pressure (BP), pulse rate (PR) or electrocardiogram (ECG) deviating from normal and assessed as clinically relevant by the investigator
- Smokers (more than 10 cigarettes or 3 cigars or 3 pipes per day)
- Alcohol abuse (intake of more than 12 g per day for females and 24 g per day for males)
- Drug abuse or positive drug screening
- Laboratory test indicative of an ongoing SARS-CoV-2 infection
- Subjects taking medications known to be inhibitors of the following drug transporters: P-gp, BCRP, OATP1B1, OATP1B3, OAT1, OAT3, MATE1, MATE2-K, OCT
- Subjects taking medications known to be moderate or strong inhibitors of the following CYP enzymes: CYP2C9, CYP2C19, CYP3A
- Subjects taking medications known to be moderate or strong inducers of the following CYP enzymes: CYP2C9, CYP2C19, CYP3A

Test product(s) 1 Dose Mode of Administration	CRESTOR® 10 mg film-coated tablets (rosuvastatin) 1 x 1 tablet (10 mg rosuvastatin) Oral with 280 mL of water after a standardized breakfast
Test product(s) 2 Dose Mode of Administration	Lanicor® 0.25 mg tablets (digoxin) 1 x 1 tablet (0.25 mg digoxin) Oral with 280 mL of water after a standardized breakfast
Test product(s) 3 Dose Mode of Administration	MetfoLiquid GeriaSan®, 1000 mg/5 mL oral solution (metformin) 1 x 0.05 mL oral solution (10 mg metformin) Oral with 280 mL of water after a standardized breakfast
Test product(s) 4 Dose Mode of Administration	Lasix® liquidum 10 mg/mL oral solution (furosemide) 1 x 0.1 mL oral solution (1 mg furosemide) Oral with 280 mL of water after a standardized breakfast
Comparator product(s)	NA
Duration of treatment	Rosuvastatin, digoxin, metformin and furosemide are given always together as a cocktail (the cocktail). The cocktail will be given as a single dose.
Statistical methods	The pharmacokinetics of each of the cocktail components rosuvastatin, digoxin, metformin and furosemide will be estimated in F4 liver cirrhosis patients compared to healthy subjects, based on the ratio (F4 liver cirrhosis patients to healthy subjects) of the geometric means (gMeans) of the primary endpoints. Additionally, their two-sided 90 % confidence intervals (CIs) will be provided. This method corresponds to the two one-sided t-tests procedure, each at the 5 % significance level. A difference of 2-fold or more, either increase or decrease, will be determined as being a clinically significant change. The statistical model will be an analysis of variance (ANOVA) on the logarithmic scale including effects for 'group', age, and BMI. CIs will be calculated based on the residual error from the ANOVA. Descriptive statistics will be calculated for all endpoints.

FLOW CHART

Visit	Day	Planned time (relative to drug administration) [hh:min]	Approximate clock time	Event and comment	blood sample for PK and biomarker analysis	Safety laboratory testing ^{a,b}	12-lead ECG	Vital signs (BP & PR) ^a	Physical examination	Urine collection for PK and biomarker analysis	Questioning for AEs and concomitant therapy ^c
1				Screening ¹							
2				Admission to trial site							
				Snack (optional)							
				F4 Liver cirrhosis patients take their morning medication ⁴							
				Baseline examinations							
				Standardised light breakfast ^{6,9,10}							
				Empty bladder ⁵							
				Administration of cocktail ^{8,9}							
				240 mL fluid intake ⁹							
				240 ml fluid intake ⁹ / lunch ¹⁰							
				Snack (optional) ⁹							
				Dinner ^{9,10}							
				Breakfast ¹⁰ (optional) and discharge from trial site							
3				Follow-up visit 1							
4				End of trial visit ¹¹							

- 1) For more details regarding screening procedures refer to section [6.2.1](#). In short: subject must be informed and written informed consent must be obtained prior to starting any screening procedures. Screening procedures include an evaluation of safety parameters ensured by a physical examination (see section [5.2.1](#)) including the assessment of medical history and concomitant medication, the assessment of smoking and drinking habits and review of inclusion and exclusion criteria. Further tests include the examination of vital signs (see section [5.2.2](#)), safety laboratory tests (see section [5.2.3](#)) which in addition to routine blood cell count and blood chemistry consists of a viral infection examination, alcohol breath testing (section [5.2.3](#)), a urine drug screening (section [5.2.3](#)), and a urine pregnancy test for females (section [5.2.3](#)). Twelve-lead resting ECG (see section [5.2.4](#)) will be recorded using a computerised electrocardiograph. Medical examination will be performed according to section [5.2.5](#)
- 2) Urine sample analysis at this timepoint includes only a drug screening, urinalysis (Stix), urine sediment and urine creatinine and an urine pregnancy test for females (section [5.2.3](#))
- 3) Safety laboratory testing and urine sample analysis at this timepoint includes only a drug screening, a breath alcohol test, an urine pregnancy test for females test (section [5.2.3](#)) and a COVID-19 rapid test (section [10.2](#))
- 4) Date, time, and dose of concomitant medication as well as the brand names must be documented
- 5) A blank urine sample is to be obtained before cocktail administration. After providing a baseline urine sample, subjects should empty their bladder at the indicated timepoint (see "planned time" -00:05)
- 6) A standardized light breakfast (see section [4.3.1](#)) will be served 1 h 30 min before the cocktail is administered
- 7) [REDACTED]
- 8) For more information regarding drug administration see section [4.3.1](#)
- 9) From 1 h before drug intake until lunch, fluid intake is restricted to the water administered with the cocktail and an additional 240 mL of water at 2 h and 4 h after cocktail administration (mandatory). From lunch until 24 h post-dose fluid is restricted to 3000 mL (see section [4.4.2.2](#))
- 10) Meals will be given after all other procedures have been conducted

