1.3 RATIONALE FOR PERFORMING THE TRIAL

The rationale for this study is to understand whether liver cirrhosis itself, along with standard of care, can result in a change in transporter activity of P-gp, OAT1, OAT3, OCT2, MATE1, MATE2-K, OATP1B1, OATP1B3 and BCRP in F4 liver cirrhosis patients compared to healthy subjects.

Liver cirrhosis is a longitudinal disease, going from F0 through to F4 compensated then decompensated. The current published data on NASH patients suggests that MRP2 is reduced due to it being mislocated, BCRP activity is increased and OATP1B3 activity is reduced. It is not clear whether this occurs in all stages of liver cirrhosis patients or only in the most severe stages of the disease [R22-3893, R22-3889, R22-3891]. Thus, the current study is to fill this information gap.

The intention is to identify whether the pharmacokinetics of a drug, based on transporter activity, is significantly different in F4 liver cirrhosis patients on standard of care compared to that observed in healthy subjects. The overall question this study will address, is how potential drug exposures may change, depending on their routes of metabolism and/or elimination from the body in F4 liver cirrhosis patients on standard of care compared to healthy subjects.

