Rosuvastatin is a substrate of OATP1B1/OATP1B3 and BCRP. Rifampicin is a known strong inhibitor of OATP transporters. After combined administration of rifampin and rosuvastatin Lai et al. and Pruesaritanont et al. describe an about 10-13-fold increase of rosuvastatin maximum concentration (C_{max}) and a 5-fold increase of rosuvastatin area under the curve (AUC) values [[R15-4771](#), [R17-1790](#)]. This effect size could be confirmed by our cocktail validation trial 0352-2100, in which a dose of 10 mg rosuvastatin has been given together with rifampicin and was well tolerated [[c23988236-01](#)].

The administration of 10 mg rosuvastatin alone in the trial 0352-2082 resulted in a mean $AUC_{0-\infty}$ of 93.4 nM*h (=44.9 ng/mL*h) and C_{max} of 8.61 nM (4.14 ng/mL) [[c02586759-02](#)]. In a DDI study with itraconazole using single doses of 80 mg rosuvastatin Cooper et al report a rosuvastatin plasma exposure of AUC of 571 ng/mL*h and C_{max} of 61 ng/mL, that was well tolerated by healthy subjects [[R13-4572](#)] providing a safety margin of 13 (AUC) and 14.7 (C_{max}) compared to the exposure after 10 mg rosuvastatin seen in 0352-2082. This is assessed

to be sufficient to cover the potential inhibition of OATP1B1/1B3 mediated by any comedication for the F4 liver cirrhosis patients.

In patients with chronic alcohol liver disease, plasma concentrations of rosuvastatin were modestly increased. In patients with Child-Pugh A disease, C_{max} and AUC were increased by 60 % and 5 %, respectively, as compared with patients with normal liver function. In patients with Child-Pugh B disease, C_{max} and AUC were increased 100 % and 21 %, respectively, compared with patients with normal liver function

Clinical data on the effect size of a specific inhibition of BCRP are not available. Thus, the risk resulting from an increased rosuvastatin exposure following a potential combined inhibition of OATPs and BCRP by comedication cannot be assessed.

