7.1 NULL AND ALTERNATIVE HYPOTHESES

It is not planned to test any statistical hypotheses in a confirmatory sense.

The relative bioavailability of rosuvastatin, digoxin, metformin, and furosemide in compensated and decompensated F4 liver cirrhosis patients (Child-Pugh A and Child-Pugh B) compared with healthy subjects (reference) will be estimated by the ratios of the geometric means (test/reference) for all PK endpoints and their corresponding 2-sided 90 % confidence intervals (CIs) will be provided. This method corresponds to the two one-sided t-test procedure, each at the 5 % significance level. Since the focus is on estimation and not testing, a formal hypothesis test and associated acceptance range is not specified.

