#### **4. CHANGES IN THE PLANNED ANALYSIS OF THE STUDY**

All analyses as planned in the CTP will be performed and are described in more detail in this TSAP. The following changes compared to the CTP will be made:

According to the study design, the treatment groups incorrectly referred to in the CTP actually correspond to the study groups. Therefore, only the term “study group” is used in the TSAP and the citations from the CTP were corrected in the TSAP.

Smoking and drinking habits were not assessed in physical examinations as in CTP Section 5.2.5 indicated. So these will not be reported.

In Section 7.2.5 of the CTP, the analysis of laboratory data was stated twice, which could be misleading. Therefore, the citation from the CTP was corrected in the TSAP [Section 7.8.2](#) so that values outside the reference range will be flagged and the laboratory values will be analysed descriptively by study group.

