### 7.4.1 Main analysis

*The primary endpoints as specified in section 2.2 will be calculated according to the BI Standard Operating Procedure (SOP) 'Standards and processes for analyses performed within Clinical Pharmacokinetics/Pharmacodynamics' (001-MCS-36-472[sic]). The analysis will be based on the PKS and will be descriptive in nature.*

*The statistical model used for the analysis of the primary endpoints will be an analysis of variance (ANOVA) model on the logarithmic scale. That is, the PK endpoints will be log-transformed (natural logarithm) prior to fitting the ANOVA model. This model will include effects accounting for the following sources of variation: '[study] group', age, and BMI. All effects will be considered as fixed. The model is described by the following equation:*

$$y_{km} = \mu + \pi_k + age_m + BMI_m + e_{km},$$

where

- $y_{km}$  = logarithm of response measured on subject  $m$  [from study group]  $k$ ,
- $\mu$  = the overall mean,
- $\pi_k$  = the  $k$ th [study] group effect, i.e. degree of hepatic impairment,  $k=1$  for healthy/normal (Group 1), 2 for Group 2 [Child-Pugh A] or 3 for Group 3 [Child-Pugh B] respectively,
- $age_m$  = the age of subject  $m$ ,
- $BMI_m$  = the BMI of the subject  $m$ ,
- $e_{km}$  = the random error associated with the  $k$ th [study] group effect for subject  $m$
- where  $e_{km} \sim N(0, \sigma_k^2)$  i.i.d,

*Point estimates for the ratios of the geometric means (test [T]/reference [R]) for the primary endpoints (see section 2.2) and their two-sided 90 % confidence intervals (CIs) will be provided [where reference is healthy subjects and the test group are the individual patient groups].*

[figure not shown]
*For each endpoint, the difference between the expected means for  $\log(T)-\log(R)$  will be estimated by the difference in the corresponding adjusted means (Least Squares Means).*

*Additionally, their two-sided 90% confidence intervals will be calculated based on the residual error from the ANOVA and quantiles from the t-distribution. These quantities will then be back-transformed to the original scale to provide the point estimate and 90 % CIs for each endpoint.*

Note: 001-MCS-36-472 = BI-KMED-TMCP-HTG-0025 & BI-KMED-TMCP-MAN-0014 ([4](#), [5](#); BI SOP was replaced).

All parameters are calculated and analysed descriptively by study group in addition to the model-based approach.

These analyses will be based on the PKS.

[figure not shown]

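### Does the synopsis's 2-fold benchmark for clinical significance conflict with an analysis section that specifies no acceptance range?

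*Protocol*

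**What the plan says.** The primary objective in the protocol synopsis asks whether Cmax and AUC0-24 of the four cocktail drugs "are similar or different in F4 graded liver fibrosis (cirrhosis) patients on standard therapy compared to healthy subjects". Under Statistical methods, the synopsis bases the comparison on the ratio of geometric means, adds two-sided 90% confidence intervals, notes that these correspond to two one-sided t-tests at 5%, and then states: "A difference of 2-fold or more, either increase or decrease, will be determined as being a clinically significant change".

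Protocol 7.1 plans no confirmatory test. It gives the same ratios and intervals and explains that, because the aim is estimation, "a formal hypothesis test and associated acceptance range is not specified". Protocol 7.2.2 and SAP 7.4.1 call the primary analysis descriptive and give the model. The SAP adds which ratios are meant: "where reference is healthy subjects and the test group are the individual patient groups". Neither section mentions 2-fold in its visible text, and nor does the sample size section, Protocol 7.5. SAP Section 4 says "All analyses as planned in the CTP will be performed and are described in more detail in this TSAP", and its list of changes does not mention the benchmark.

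Protocol 1.4.2.3 gives background figures for rosuvastatin in chronic alcohol liver disease: "In patients with Child-Pugh A disease, C_{max} and AUC were increased by 60 % and 5 %, respectively" and "In patients with Child-Pugh B disease, C_{max} and AUC were increased 100 % and 21 %, respectively".

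**The concern.** Three things make this look like a fault. First, the synopsis promises a determination that no visible analysis section carries out or withdraws. Secondly, the 2-fold sentence comes straight after the reference to two one-sided tests. A reader could therefore apply it to the point estimate or to the whole confidence interval, and the plan does not say which. Protocol 1.3 adds to this by asking whether pharmacokinetics "is significantly different in F4 liver cirrhosis patients on standard of care compared to that observed in healthy subjects", without tying that to any size. Thirdly, the protocol's own background figure for rosuvastatin Cmax in Child-Pugh B is an increase of 100%. That is a ratio of exactly 2.00, on the boundary, and it concerns the group with only 6 patients.

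At stake would be the wording of a primary result. If the reading is open, someone writing the report could choose it after seeing the data.

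**Working it through.** **The passages side by side.** An acceptance range is the set of values within which a test's interval must fall. Protocol 7.1 says there is none. The synopsis names a size of change that counts as clinically important. A trial can estimate ratios, test nothing, and still say in advance what size matters. Section 7.1 in fact helps to settle the reading: with no acceptance range, 0.50 to 2.00 cannot be equivalence limits for the interval. What remains is a benchmark for the estimated ratio, which is also the quantity on which the synopsis bases the comparison.

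**Is there a figure to reproduce?** No. The plan gives no power or precision calculation, so the check below only asks how much the choice of reading could matter.

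**Inputs.** Group sizes of 12, 12 and 6 (Protocol 7.5); three group effects and two covariates (Protocol 7.2.2); background increases in Protocol 1.4.2.3. The between-subject geometric CV is not in the documents, so 30%, 50% and 80% are assumed. A common variance is also assumed, and precision lost to the age and BMI adjustment is ignored.

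**Formulas.**
- Log-scale SD = sqrt(ln(1 + CV²)) = 0.294 / 0.472 / 0.703
- SE = SD × sqrt(1/12 + 1/n), with n = 12 (Child-Pugh A) or 6 (Child-Pugh B)
- Residual df = 30 − 3 − 2 = 25, so t(0.95) = 1.708
- Interval factor = exp(t × SE)

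For Child-Pugh B at 50%: SE = 0.472 × 0.5 = 0.236; t × SE = 0.403; factor = 1.50. An observed ratio of 2.00 then has a 90% interval of 1.34 to 2.99.

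| Assumed CV | Factor, A | Factor, B | Readings differ for observed ratios, A | Readings differ for observed ratios, B |
|---|---|---|---|---|
| 30% | 1.23 | 1.28 | 2.00–2.45 | 2.00–2.57 |
| 50% | 1.39 | 1.50 | 2.00–2.78 | 2.00–2.99 |
| 80% | 1.63 | 1.82 | 2.00–3.27 | 2.00–3.65 |

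Between 0.50 and 2.00 both readings withhold the label. Above the upper end of each range both give it. Reciprocals apply to decreases.

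**How often the label appears.**
- True ratio 1 + 1.00 = 2.00: the point estimate reaches 2.00 in 50% of trials, because it is symmetric around the truth on the log scale. The whole 90% interval lies at or above 2.00 in 5%. Neither figure depends on the CV.
- True ratio 1.60 (Child-Pugh A Cmax): 3 / 12 / 22% on the point estimate.
- True ratio 1.21 (Child-Pugh B AUC): 0.0 / 1.7 / 8.2%.
- True ratio 1.05 (Child-Pugh A AUC): 0.0 / 0.0 / 1.7%.
- True ratio 1.00, Child-Pugh B, upward label only: 0.0 / 0.2 / 2.4%.

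**What the 50% means.** Any cut-off is crossed half the time when the truth lies on it, so this figure says nothing specific about this plan.

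**How much rests on the boundary case.** There are 4 drugs × 2 parameters × 2 patient groups = 16 primary comparisons. The 2.00 concerns one of them. It comes from a risk section, describes chronic alcohol liver disease, and compares with patients who have normal liver function. This trial enrols cirrhosis of any cause, excludes alcohol intake above 12 g (women) or 24 g (men) per day, and compares with healthy subjects matched where feasible. The protocol does not offer the figure as its expected result.

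**The case for a change.** The strongest case for a change is that 2-fold is the only visible size benchmark for a primary objective phrased as similar or different, and that one sentence in Protocol 7.2.2 and one in SAP 7.4.1 would fix its meaning at almost no cost. The SAP records changes as small as renaming treatment groups to study groups, so silence on the benchmark looks like an oversight. A label whose meaning is unwritten can be settled after the data are seen.

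Part of this stands. The visible body text does not repeat the benchmark, and nowhere is it written that it applies to the adjusted ratio.

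The rest is weaker. The undertaking in SAP Section 4 concerns analyses, and a label attached to a reported ratio is interpretation. SAP Section 3 sends readers to the protocol for objectives. The SAP contents list has a redacted entry between 7.4.1 and 7.5, so absence from the SAP as a whole cannot be shown. A late choice of reading would also be visible, because every primary ratio carries its interval. SAP Section 7 already warns that results need caution given the exploratory aim and small groups. The phrase in Protocol 1.3 is ordinary prose in a rationale and sets no rule.

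**Conclusion.** No change follows. The synopsis benchmark and the absence of an acceptance range are compatible, and analysts will fill the small gap sensibly: report each patient-group-to-healthy ratio with its 90% interval, and note where the ratio is 2.00 or more, or 0.50 or less. The most that depends on the reading is one descriptive label, for observed ratios in a band that starts at 2.00 and ends between 2.45 and 3.65 depending on group and assumed CV (30 to 80%). No estimate, interval, error rate or sample size moves.

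The alternatives gain nothing. Copying the sentence into Section 7 writes down what a reader already infers; it would be harmless if the texts were reopened for another reason. Deleting it would leave an exploratory trial without its one visible pre-stated size benchmark.

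The band widths rest on the assumed CVs, a common variance and no loss of precision from covariate adjustment. The conclusion does not depend on them, because it follows from what the passages say.
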